The potential benefit of participation is high, as changes in antipsychotic medication and appropriate cardiovascular risk screening and management will result in decreased cardiovascular risk.

Burden and risk associated with outcomes measurements:

Patients fill in questionnaires at baseline and every 5 months during follow-up. Based on our experiences in the pilot study, we expect that it will take approximately 20 minutes to fill in

the questionnaire. For the assessment of the primary outcome QRISK3 score routinely collected data from the cardiovascular risk management programme, i.e. blood pressure, body weight, smoking behaviour, and blood cholesterol and glucose levels.

INTRODUCTION AND RATIONALE

Antipsychotic medication is effective for a variety of psychiatric disorders, such as schizophrenia, bipolar disorder, schizoaffective disorder, or major depressive disorder. Remarkably, however, a large proportion of patients on antipsychotics do not have a diagnosis of a severe mental illness (6). Jakobs et al. found that, among patients in general practices who use antipsychotic medication, up to 68% did not have a registered diagnosis of a severe mental illness. These patients are using antipsychotics off-label. Reasons for off-label prescription can be anxiety, dementia, or sleep- and personality disorders.

The use of antipsychotic medication is increasing worldwide (1-3), but this is not without risk. It is well established that patients with a severe mental illness and patients treated with antipsychotics have excess metabolic dysfunction (4) and are at an increased risk of cardiovascular disease (4, 5). The increased risk of cardiovascular disease is multifactorial. Patients with a severe mental illness or on antipsychotic medication tend to have a high incidence of lifestyle risk factors, such as poor diet, lack of exercise, stress and smoking, besides possible genetic susceptibility (8, 9). Furthermore, there is evidence that people with severe mental illness are less likely to receive standard levels of care (5). Moreover, antipsychotics can cause weight gain, hypertension, glucose intolerance and dyslipidaemia, and can cause cardiac toxicity (10).

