Although these factors may contribute as independent risk factors for cardiometabolic dysfunction and cardiovascular disease, having a severe mental illness itself is also an important independent risk factor (5), as well as antipsychotic treatment, particularly for certain drugs and for vulnerable patients (9). In a large prospective open cohort study in England, severe mental illness was associated with a 14% increased risk for women and a 13% increased risk for men (11). This was independent of the risk associated with atypical antipsychotics. Atypical antipsychotics were associated with an increased cardiovascular risk of 29% in women and 15% in men. In addition, antipsychotics cause a dose-related increased risk of sudden cardiac death (12). All in all, this results in a 8-20 years reduction in life expectancy (11).

In the Netherlands, it is common that psychiatrists initiate treatment with antipsychotic medication, but when patients reach a stable state, care is shifted to the general practice. This includes monitoring of treatment effects, adherence and side effects, as well as management of cardiovascular risk. However, monitoring of usage and effects of antipsychotic treatment as well as cardiovascular risk screening in patients with severe mental illness or on antipsychotic treatment is currently not sufficient (5-7). Lifestyle factors

are relatively easy to measure, but are barely considered for screening. Baseline testing of important physical parameters, prior to starting antipsychotic medication, is insufficiently performed (5). This is a serious aspect that needs to be addressed, even more since the adverse effects of antipsychotic medication may also impair the patient's adherence to treatment (13).

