5. METHODS

5.1 Study parameters/endpoints

5.1.1 Main study parameters

- Our first primary outcome measure is the QRISK3 score (11). The QRISK3 algorithm (www.qrisk.org/three) calculates a person's risk of developing a cardiovascular event (e.g. a heart attack or stroke) over the next 10 years. The score presents the average risk of people with the same risk factors as those entered for that person. The QRISK3 is the preferred algorithm for assessing cardiovascular risk according to the NICE guideline Cardiovascular Disease (18). It includes severe mental illness and use of atypical antipsychotics as predictors for cardiovascular disease, which makes it suitable for use in our study.

The QRISK3 score is calculated based on age, gender, ethnicity, Townsend deprivation score, smoking status, diabetes status, having chronic kidney disease,

atrial fibrillation, migraines, rheumatoid arthritis, systemic lupus erythematosus, severe mental illness or a family history of premature coronary heart disease in a first degree relative, being on blood pressure treatment, on regular steroid tablets, or on atypical antipsychotic medication, having a diagnosis of or treatment for erectile dysfunction, levels of cholesterol/HDL ratio, systolic blood pressure, standard deviation of blood pressure, and Body Mass Index. As the Townsend deprivation score is not applicable to the Dutch population, we will set this to 0, meaning neither deprived nor affluent, as is advised by the authors. The QRISK3 score can range from 0 to 100%. We consider a decrease of 2.5%-points as clinically relevant.

- Our other primary outcome measure is the Mental Health Inventory, five-item version (MHI-5), which is a measure for the mental quality of life (19). The MHI-5 is a derivative of the 36-item short form health survey, the SF36, and assesses symptoms of depression and anxiety, loss of behavioural or emotional control, and psychological well-being in the prior four weeks. The MHI-5 ranges from 0 to 100, where a score of 100 equals perfect mental health. A score of 60 or higher is seen as good mental health, whereas a score below 60 is seen as poor mental health. We will consider an increase of 5 points as clinically relevant.

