5.3 Study procedures

After enrolment of the general practice, a list with all eligible patients will be generated in VIPlive. A computerized programme will randomly select 30 eligible patients per general practice, who will receive a letter from their general practitioner, informing the patient about the upcoming trial. Patients will be invited to contact the general practice when they are interested in participation. An appointment for a regular cardiovascular risk management consultation at the general practice will then be made. Patients who did not reply to the letter, will be contacted by phone. In the context of the existing regional cardiovascular risk management programme patients will undergo physical examination (for measuring length, weight and blood pressure), venapuncture and urinalysis (for measuring risk factors, i.e. HbA1c, blood glucose, lipid spectrum and kidney function), and will be asked about their ethnicity, smoking status and family history of coronary heart disease. All other information will be derived from their medical file, e.g. having atrial fibrillation, migraines, or rheumatoid arthritis. In addition to the usual SCORE calculation, the QRISK score will also be calculated specifically for this study. When the QRISK3 score is below 5%, the patient does not meet the inclusion criteria and will be followed by the general practitioner according to the regular cardiovascular risk management

programme. Patients with a QRISK3 $\geq 5\%$ will be invited to sign informed consent for participation in the TACTIC intervention study.

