7.1 Primary study parameters

As mentioned in chapter 6.1.1, the QRISK3 score is calculated based on several parameters that are collected during regular cardiovascular risk management consultations as part of usual care. For age, we will use age at baseline (T0) at all measurement points. Since the QRISK3 score cannot be calculated when individual items are missing, we will use the following values:

- In case ethnicity is missing, we will use “white or not stated”.

- In case smoking status is missing, we will use “non-smoker”.
- In case the patient is a smoker, but the amount of cigarettes is not stated, we will use “moderate (10-19)”.
- In case cholesterol/HDL ratio is missing, we will use 4.4 for men and 3.7 for women (11). In case systolic blood pressure is missing, we will use the latest measurement of this value, or, if no measurements are available, we will use 129mmHg for men and 123mmHg for women (11).
- In case standard deviation of systolic blood pressure is missing, we will use “0”.
- In case either weight or both length and weight are missing, we will use the latest measurement of the Body Mass Index, or, if no BMI is available, we will use Body Mass Index values as mentioned in table 2.
- In case only length is missing at all measurement points, we will use values as mentioned in appendix ... for calculating Body Mass Index.
- In case calculated Body Mass Index is $<20\text{kg/m}^2$, the value is set to 20kg/m^2 , as the algorithm is not validated for values of Body Mass Index lower than 20kg/m^2 .

Age (years)	Men	Women
25-39	25.2	24.4
40-49	26.2	24.7
50-59	26.5	25.7
60-84	26.8	26.4

Table 2. Mean Body Mass Index (kg/m^2) by age and gender, based on RIVM 2012.

- In case family history of premature coronary heart disease in a first degree relative is “yes” at any measurement point, all measurement points will be set to “yes”, as this factor might not be manifest at the start of enrolment, but does contribute to the patient’s cardiovascular risk, regardless to the moment this factor becomes manifest. This also applies for the factors migraines, rheumatoid arthritis, systemic lupus erythematosus, and erectile dysfunction.
- In case a patient starts blood pressure treatment due to the intervention, all prior measurement points will be set to “yes”, as the indication for blood pressure treatment would have been present provided the patient was on appropriate usual care.

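### The QRISK3 back-dating list leaves out severe mental illness, so a long-standing illness first registered after the TACTIC meeting can raise post-TACTIC scores

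*Protocol*

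**What the plan says.** Section 5.1.1 of the protocol lists the QRISK3 inputs. They include chronic diagnoses: "The QRISK3 score is calculated based on age, gender, ethnicity, Townsend deprivation score, smoking status, diabetes status, having chronic kidney disease", followed by "atrial fibrillation, migraines, rheumatoid arthritis, systemic lupus erythematosus, severe mental illness or a family history of premature coronary heart disease".

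Section 7.1 says how some of these are harmonised over time. A family history of premature coronary disease that is positive at any measurement point is made positive at all of them. The reason given is that it may not yet be apparent at enrolment "but does contribute to the patient’s cardiovascular risk, regardless to the moment this factor becomes manifest". The rule is then extended: "This also applies for the factors migraines, rheumatoid arthritis, systemic lupus erythematosus, and erectile dysfunction". A further rule covers treatment: "In case a patient starts blood pressure treatment due to the intervention, all prior measurement points will be set to" *yes*, on the argument that the indication would already have existed under proper usual care.

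Section 7.1 has no such rule for severe mental illness, diabetes, chronic kidney disease or atrial fibrillation.

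On the source of the diagnosis flags, section 5.3 says of the entry visit: "All other information will be derived from their medical file, e.g. having atrial fibrillation, migraines, or rheumatoid arthritis". Section 4 states that patients serve as their own control before treatment starts, and that a psychiatrist takes part in the Step 2 multidisciplinary meeting.

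**The concern.** The list exists so that a condition which was there all along, but was noticed late, does not look like a change in risk. SMI fits that purpose at least as well as migraine does. Patients must have used an atypical antipsychotic for at least 3 months at baseline (section 3.2), so an SMI first registered during follow-up may well predate entry.

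SMI also differs from the listed factors in one respect: TACTIC itself adds a psychiatrist to the patient's care, and usual care does not. If that review leads the practice to register an existing SMI, the flag is *no* before TACTIC and *yes* after it. In a within-patient comparison this counts as a rise in predicted risk under the intervention, although the patient's health is unchanged. The time term in the section 7.1 model would not remove it, because the change follows the intervention and not the calendar.

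The first primary outcome would then understate any benefit of TACTIC.

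**Working it through.** The plan states no figure on this point, so there is none to reproduce. The check is a comparison of two lists, followed by a sizing.

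**1. List comparison**

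| QRISK3 input (5.1.1) | Back-dated in 7.1? |
|---|---|
| Family history, migraine, rheumatoid arthritis, lupus, erectile dysfunction | Yes, if positive at any point |
| Blood pressure treatment | Yes, to prior points, if started due to the intervention |
| Severe mental illness | No rule |
| Diabetes, chronic kidney disease, atrial fibrillation | No rule |

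A rule triggered by a positive entry at any measurement point presupposes that flags can differ between points. Without a rule, an SMI flag can do the same.

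**2. Size of one new SMI flag**

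The weight comes from the Introduction: "severe mental illness was associated with a 14% increased risk for women and a 13% increased risk for men". I read it as a hazard ratio *h* of 1.13 (men) or 1.14 (women). For a patient with score *r* before the flag:

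rise in points = 100 × {[1 − (1 − r)^h] − r}

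| Score before flag | h = 1.13 | h = 1.14 |
|---|---|---|
| 5% (entry threshold, section 3.2) | +0.63 | +0.68 |
| 10% | +1.22 | +1.32 |
| 15% | +1.78 | +1.91 |
| 20% | +2.29 | +2.46 |

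Reading the weight as a plain multiplier changes little. At 10% it gives 10 × 0.13 = 1.3 to 10 × 0.14 = 1.4 points.

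**3. Effect on the mean**

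mean shift = share of patients newly coded × rise per patient

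The protocol gives neither the share newly coded nor the distribution of scores. Both are assumptions here: shares of 5–20% and scores of 10–20%.

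- Low end: 0.05 × 1.22 = 0.06 points
- High end: 0.20 × 2.46 = 0.49 points

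Against the 2.5-point target (sections 3.4 and 5.1.1), this is 0.06/2.5 = 2% to 0.49/2.5 = 20%.

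**4. After the change**

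With SMI on the list, the flag is the same at every point for a given patient, so newly registering it contributes no change between points.

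**The case against.** **New SMI coding is an inference.** Section 4 describes Step 2 as a 15-minute review of medication and cardiovascular risk factors that ends in treatment suggestions. It mentions no re-diagnosis, and the psychiatrist works from the practice's existing record. This stands. The documents show that late registration is possible, not that it will happen or how often.

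**The 68% figure does not measure missed SMI.** The Introduction reports that among antipsychotic users in general practice "up to 68% did not have a registered diagnosis of a severe mental illness". A reader might take this as the pool waiting to be coded. The same paragraph describes these patients as off-label users, for reasons such as anxiety, sleep or personality disorders. It cannot serve as an estimate of the share newly coded.

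**Diabetes and kidney disease.** A reader might extend the argument to these, since HbA1c, glucose and kidney function are tested at entry. The documents do not support that as a TACTIC-specific bias. The tests are usual care, they precede the entry QRISK3 score, and they recur every five months (section 5.3). Disease they reveal can already count at entry. Any coding delay would fall only on TACTIC measurements under a particular layout of control points, and Figure 1 is not available to confirm one. New diabetes may also be real change: the Introduction names glucose intolerance as a drug effect and prevention of type II diabetes as a goal. A mean shift of 0.38–0.57 points can be built at a score of 15% by assuming that 10% of patients gain an SMI code and 3% a diabetes or kidney code with a ratio of 1.5–2.0 (0.10 × 1.78 + 0.03 × 6.63 = 0.38; 0.10 × 1.91 + 0.03 × 12.75 = 0.57). Those shares and ratios are not in the protocol, and half or more of the result comes from the diabetes and kidney part.

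**Follow-up extraction of diagnoses is not described.** The medical-file sentence in section 5.3 concerns the entry visit. That is true, but section 7.1 itself allows flags to differ between points, so the case has to be covered.

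**The bias is conservative.** It works against TACTIC and would not create a false benefit. This also stands. It lowers the urgency but does not remove the inconsistency.

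**Conclusion.** The omission is real, and it conflicts with the reason section 7.1 gives for its own list. For SMI it leaves open a path by which post-TACTIC scores *can* rise through registration alone. It would be too strong to say that they *will* rise.

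For one patient the artefact is about 0.6–0.7 points at a score of 5%, 1.2–1.3 at 10% and 2.3–2.5 at 20%, using the protocol's own SMI weight as a hazard ratio. The last figure is close to 2.5 points, but that target is a difference in means, so the two are not comparable. On the mean, the shift is about 0.06–0.49 points if 5–20% of patients are newly coded at scores of 10–20%. Both ranges are assumptions, and the true shift could be negligible. The direction is against TACTIC. A reader might also expect the reverse bias, from diagnoses removed after review, but nothing in the protocol points to that.

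The finding for the primary analysis is limited to SMI. Diabetes, chronic kidney disease and atrial fibrillation are also unlisted, but they warrant no more than a sensitivity analysis.

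**What to change.** In section 7.1:

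1. Add severe mental illness to the factors for which a positive entry at any measurement point makes all points positive.
2. For diabetes, chronic kidney disease and atrial fibrillation, state that the primary analysis uses the status as recorded at each point, because new onset may be real change.
3. Add a sensitivity analysis of the QRISK3 outcome with those three flags held constant across each patient's measurement points, and state in advance which value is held.

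The cost is a few lines in the score derivation and one extra model run, with no new data. Deriving diabetes or kidney disease from each visit's laboratory values is not proposed, because it would need diagnostic thresholds that the protocol does not contain.

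The downside of item 1 is that a truly new SMI diagnosis during follow-up is also back-dated. The protocol already accepts the same trade-off for the conditions now on its list. The change should be fixed before outcome data are analysed, since recoding a primary outcome afterwards would look selective.

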After signed informed consent and inclusion, baseline measurement will take place and patients will fill in a digital questionnaire using Castor EDC, containing MHI-5, EQ-5D-5L, TIC-P and LUNSERS. As part of the preparation for the multidisciplinary meeting, patients will be asked to fill in a custom-made questionnaire on antipsychotic use. This questionnaire will help healthcare professionals prepare for the meeting and will give the patient insight in possible topics that can be addressed during the meeting. In case patients do not have an email address, we will send the questionnaires by mail. Patients will then watch the information video at home, attend the multidisciplinary meeting, and attend a consultation with their general practitioner, as described in section 5. At five months follow-up, patients will be invited for follow-up (monitoring) measurements at the general practice as part of the regular regional cardiovascular risk management programme (usual care), to undergo physical examination (measuring weight and blood pressure), venapuncture and urinalysis (for measuring risk factors, i.e. HbA1c, blood glucose, lipid spectrum and kidney function). As part of the evaluation, patients will also fill in questionnaires, containing MHI-5, EQ-5D-5L, LUNSERS, TIC-P and general questions about smoking status and family history of coronary heart disease. Depending on which step the cluster has started, patients will undergo one to four follow-up measurements, every five months. This is in line with the routine check-ups patients will have in the regular cardiovascular risk management programme. During the last follow-up measurement, they are also asked to fill in the CSQ-8. Table 1 presents the schedule of assessments.

No diagnostic procedures or treatment will be postponed.

	Visit general practice	Digital information	Physical examination	Laboratory tests	Questionnaires
Week 1 Routine screening and inclusion after informed consent	X		X	X	
Week 2 Baseline measurement					X
Week 3 Information video		X			
Week 4/5	X				

Multidisciplinary meeting					
Week 5/6 Consultation with GP	X				
Month 5 Routine consultation as part of usual care. Follow-up measurement 1 Start Step 2 at Week 1	X		X	X	X
Month 10 Routine consultation as part of usual care. Follow-up measurement 2 Start Step 3 at Week 1	X		X	X	X
Month 15 Routine consultation as part of usual care. Follow-up measurement 3 Start Step 4 at Week 1	X		X	X	X

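### QRISK3 blood pressure treatment is back-dated only for starts attributed to TACTIC, so a primary outcome is recoded by condition and by an unblinded judgement of cause

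*Protocol*

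**What the plan says.** Section 5.1.1 makes QRISK3 the first primary outcome and lists among its inputs "being on blood pressure treatment, on regular steroid tablets, or on atypical antipsychotic medication". Section 7.1 opens by stating that "the QRISK3 score is calculated based on several parameters that are collected during regular cardiovascular risk management consultations as part of usual care", and then lists coding rules. Three of them matter here:

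- Blood pressure treatment: "In case a patient starts blood pressure treatment due to the intervention, all prior measurement points will be set to “yes". The reason given is "as the indication for blood pressure treatment would have been present provided the patient was on appropriate usual care".
- Family history, and with it migraines, rheumatoid arthritis, lupus and erectile dysfunction: once present at any point, coded present at all points, "regardless to the moment this factor becomes manifest".
- Age: "For age, we will use age at baseline (T0) at all measurement points".

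Section 4 names starting antihypertensive medication as a possible Step 3 action and treats patients as their own comparator before the intervention. According to the Summary and section 4, all participants are in the regular cardiovascular risk programme and TACTIC comes on top of it. Section 5.3 describes the follow-up visits as "measurements at the general practice as part of the regular regional cardiovascular risk management programme (usual care"). Section 5.2 says that clusters cannot be blinded.

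**The concern.** A start can be attributed to TACTIC only after the cluster has crossed over. By construction, then, the rule treats starts differently in the two conditions, and within the intervention condition it separates them by judged cause. The protocol gives no criterion for that judgement and names nobody to make it.

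Routine starts are to be expected, because usual care is itself a risk management programme with five-monthly checks. After crossover, routine starts and TACTIC starts occur side by side. The stated reason, that the indication was already there, can apply to a routine start too. Of the coding rules in section 7.1, this is the only one that depends on attribution to the intervention.

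At stake is a primary outcome. Each label decides whether a patient shows no change or a rise in predicted risk, and a positive label alters that patient's control-period values after the fact.

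**Working it through.** The plan states no figure to reproduce, so the check asks how far the label can move the estimate.

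**From the protocol:** 32 clusters in four steps (8 per step), 12 analysed patients per cluster, ICC 0.10, within-patient correlation about 0.95, relevant difference 2.5 points.

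**Assumed, because the protocol does not give them:** *yes* raises the score; baseline risk 15%; routine starts h = 3-5% per five months in both conditions; starts caused by TACTIC e = 10 percentage points in the first interval after it; no true effect and all other inputs unchanged.

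**Weight w of the treatment item.** With hazard ratio HR, the score becomes 1 - 0.85^HR.
- HR 1.2: 17.72%, so w = 2.72 points.
- HR 1.6: 22.90%, so w = 7.90 points.

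**One patient.** Start attributed to TACTIC: 17.72 before and 17.72 after, change 0. Same start not attributed: 15.00 then 17.72, change +2.72. In a cluster of 12, one label moves the mean change by 2.72/12 = 0.23 points (7.90/12 = 0.66 at the larger weight).

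**Whole trial.** The model is generalised least squares with fixed time effects, one condition effect, and random cluster and patient effects. With all clusters measured at 0, 5, 10, 15 and 20 months, as-recorded routine starts give the same rise in every step, and the time effects absorb it. What remains is a step at crossover:

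shift = w × [(1 - a) × e - b × h]

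Here a is the share of caused starts that are labelled and b the share of routine first-interval starts that are labelled. Positive counts against TACTIC.

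| Labelling | Calculation | Shift (points) |
|---|---|---|
| Nothing back-dated (a = b = 0) | 2.72 × 0.10; 7.90 × 0.10 | +0.27 to +0.79 |
| Only caused starts (a = 1, b = 0) | w × 0 | 0.00 |
| All first-interval starts (a = b = 1) | -2.72 × 0.03; -7.90 × 0.05 | -0.08 to -0.40 |
| Half of first-interval starts (a = b = 0.5) | 2.72 × (0.05 - 0.025); 7.90 × (0.05 - 0.015) | +0.07 to +0.28 |

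**Other layout.** Section 5.3 says "Depending on which step the cluster has started, patients will undergo one to four follow-up measurements, every five months". This suggests one control measurement per cluster, followed by 4, 3, 2 or 1 follow-ups; the design figure is not available. The same model then gives +0.27 to +0.80, within 0.01 of 0, -0.08 to -0.39, and +0.07 to +0.28, in the order of the table.

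**Sensitivity of these results.**
- If start rates apply only to patients not yet treated, correct labelling gives up to +0.09 and half labelling up to +0.32.
- If every start after crossover is labelled, the full layout gives -0.04 to -0.19 and the one-control layout is within 0.01 of zero.
- With w about 1 point and no caused starts, labelling all first-interval starts gives -0.03 to -0.05.
- A separate simulation with wider assumptions (routine starts 2-10%, caused starts 10-30%, item weight 20-60% of a 15% score) gave 0.00 to -0.10 with correct labels, about +0.1 to +1.2 when half of the caused starts were missed, and -0.03 to -0.41 when every start after crossover was labelled.

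**Cause-free coding.** Back-dating every start is within 0.01 of zero in both layouts. Using the baseline value gives exactly 0.

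**The case against.** The strongest reply is that the rule, applied as written, works. If TACTIC uncovers under-treatment, as-recorded coding would count the extra starts against it, by 0.27 to 0.80 points above. Labelling only truly caused starts removes almost all of that. This stands: the rule is better than no rule, and any appreciable bias needs wrong labels.

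Several stronger readings do not stand.

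- A reader might infer that the rule favours TACTIC. That follows only if routine first-interval starts are labelled as caused. Missed labels push the other way, and the documents do not show which would prevail.
- A reader might say that other starts have no rule. The opening of section 7.1 supplies a default, coding as collected. The fault is an inconsistent rule rather than a missing one.
- A reader might say that the stated reason fits every routine start equally. It need not: an indication may have newly arisen, and the earlier *no* was then correct. Family history is also not a treatment decision, so that parallel is imperfect.

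Section 5.1.2 records the advice given in Step 3 and whether it was carried out, which offers some basis for attribution, and an SAP could define the term. But a record that a start followed advice does not show that the routine check would not have led to it. The one-sided rule is fixed in the protocol and would remain.

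Finally, section 7.1 plans a time-by-group interaction, which the calculation omits. The figures show scale and are not a prediction for the planned model.

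**Conclusion.** The point holds as a flaw in coding. A primary outcome, control-period values included, is recoded according to condition and an undefined, unblinded judgement of cause. With correct attribution the rule is within about 0.1 point of zero. Plausible misattribution moves the estimate by about 0.08-0.40 points towards TACTIC or about 0.07-0.3 against it. Against 2.5 points that is roughly 3-16% (0.08/2.5 to 0.40/2.5) and 3-12% (0.07/2.5 to 0.3/2.5).

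These sizes rest on the assumed item weight, start rates and layout, and on a model without the interaction. No direction of bias is established. The change is worth making because the dependence on attribution is unnecessary and cheap to remove, not because a large bias has been shown. Confidence is medium.

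**What to change.** Replace the bullet in section 7.1 by a rule that ignores condition and cause, for example:

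> If blood pressure treatment starts at any measurement point, for any reason and in either condition, all measurement points are set to yes.

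Alternatively, use the baseline value of this item at all points for all patients, as is already done for age. Apply the same coding in the responder analysis of section 7.3. Report QRISK3 with treatment status as recorded as a sensitivity analysis, noting that it counts extra starts caused by TACTIC against TACTIC.

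The cost is one edited bullet and one added analysis, with no new data and no change to care. The drawback is that genuine changes in treatment status are overwritten (back-dating) or ignored (baseline value) in both conditions. Back-dating also shifts analysed baselines, as the present rule already does for labelled patients.
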